## 8.2.7 CLINICAL SAFETY LABORATORY ASSESSMENTS

See [Appendix 11](#) for the list of clinical laboratory tests to be performed and the SoA ([Section 1.3](#)) for the timing and frequency of the tests.

A central laboratory will be used to perform all laboratory tests except urine pregnancy dipstick which will be assessed by the study site staff. However, local laboratory tests will be allowed in the event that the central laboratory results will not be available immediately and the Investigator needs to make an immediate decision for any safety concerns based on laboratory results. If a local sample is required, it is important that the sample for central analysis is obtained at the same time.

The Investigator must review the laboratory report, document this review, and record any clinically relevant changes occurring during the study in the AE section of the eCRF. The laboratory reports must be filed with the source documents. Clinically significant abnormal laboratory findings are those that are not associated with the underlying disease, unless judged by the Investigator to be more severe than expected for the subject's condition.

All laboratory tests with values considered clinically significantly abnormal during the study and including the subject's last study visit (EOS) should be repeated until the values return to normal or Baseline or are no longer considered clinically significant or judged medically stabilized by the Investigator or Medical Monitor.

If such values do not return to normal/Baseline within a period of time judged reasonable by the Investigator, the etiology should be identified, and AnaptysBio notified.

All protocol-required laboratory assessments, as defined in [Appendix 11](#), must be conducted in accordance with the Laboratory Manual and the SoA.

If laboratory values from non-protocol specified laboratory assessments performed at the institution's local laboratory require a change in subject management or are considered clinically significant by the Investigator (eg, SAE or AE), then the results must be recorded in the eCRF.

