#### 9.4.8.2 12-LEAD ELECTROCARDIOGRAM, VITAL SIGNS, AND CLINICAL SAFETY LABORATORY TESTS

Summaries and listings of data for vital signs and safety laboratory tests result (hematology, biochemistry, and urinalysis) will be presented. Appropriate descriptive statistics will be summarized for the observed value at each scheduled assessment and for the corresponding change from Baseline.

For hematology and biochemistry tests, listings of subject data will also flag up any abnormal or out-of-range values. Clinically significant changes in the laboratory test parameters will be summarized and listed. Hematology and biochemistry data will be reported in System International units.

Descriptive statistics will be used to present the safety outcomes including, weight, BMI, 12-Lead ECG, vital signs, and clinical laboratory test results.

Change from Baseline will also be summarized for vital signs, and clinical laboratory tests results.

All ECG data results (normal/abnormal) will be summarized using frequency and percentage, and parameter values will be summarized descriptively. Clinically significant abnormalities will be presented in by-subject listings.

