### 6.6.1 Study Day and Visit Window Definitions

Adverse Events will be closely monitored on each patient throughout their participation in the study. Adverse Events will be reported by the study period that they occurred in as detailed in the Data Handling Rules Appendix. Safety assessments for other safety variables will occur as detailed in the Schedule of Activities in **Section 3.6**. Safety data assessed per the Schedule of Activities will be allocated according to the rules for efficacy data in **Section 6.2.1**.

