### Use of Data from Unscheduled Assessments for Laboratory, ECG and Vital Sign Summaries (Continuous Parameters)

Data from unscheduled visits will be listed; duplicate unscheduled measurements will not be shown twice. If the data from the scheduled visit is missing, data from unscheduled visits that fall in the visit window of the same scheduled visit will be used. In cases where there are multiple unscheduled visits, the most recent unscheduled visit will be used.

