### 7.9.3 Laboratory Data

Summary statistics (n, mean, median, standard deviation, minimum, and maximum) for the baseline assessment and for the observed value and change from baseline at each post-baseline visit for scheduled lab assessments of continuous laboratory variables will be tabulated. Shift tables (e.g., tables that show the number of subjects who are low, normal, or high at baseline versus each post-baseline scheduled assessment) will be produced.

If there are multiple laboratory values for the same parameter at a given visit, the last value will be chosen for analysis.

All data will be displayed in patient data listings for Safety Analysis Set.

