### 7.9.5 Electrocardiogram (ECG)

ECG data (Heart Rate, PR Interval, RR Interval, QRS Interval, QT Interval, and QTcF Interval) will be tabulated with descriptive statistics by visit for both the raw values as well as the changes from baseline.

Number and percentage of subjects with clinically significant abnormalities in all ECG parameters will be summarized for normal, abnormal - not clinically significant and abnormal - clinically significant categories by treatment group. Three-by-three contingency tables will be presented to summarize the shift from the baseline category to the worst post-baseline value. Summary results will include the count and percentage of subjects within each shift category and treatment group.

If there are multiple ECG values for the same parameter at a given visit, the last value will be chosen for analysis.

All ECG data as well as clinically significant abnormalities will be presented in by-subject listings.

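### The SAP specifies no baseline-to-worst laboratory shift and drops a summary the protocol promises, so some out-of-range values reach no by-arm laboratory table

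*SAP*

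**What the plan says.** **Laboratory tables.** SAP 7.9.3 plans by-visit summary statistics and shift tables, described by example as counts of subjects "low, normal, or high at baseline versus each post-baseline scheduled assessment". For several results at one visit: "If there are multiple laboratory values for the same parameter at a given visit, the last value will be chosen for analysis".

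**Unscheduled values.** SAP 7.9 lists them all. On their use in summaries it says "If the data from the scheduled visit is missing, data from unscheduled visits that fall in the visit window" will be used, and "In cases where there are multiple unscheduled visits, the most recent unscheduled visit will be used". SAP 6.6.1 gives another route: "Safety data assessed per the Schedule of Activities will be allocated according to the rules for efficacy data". Those rules, in SAP 6.2.1, also turn to unscheduled data only when the nominal-visit value is missing or outside its window, but then take the nearest measurement on or before the nominal day.

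**Repeat testing.** Under Protocol 8.2.7, tests with clinically significantly abnormal values "should be repeated until the values return to normal or Baseline", or until they are no longer clinically significant or are judged stable. Protocol Section 8 also allows repeat or unscheduled samples for safety reasons or for technical problems with a sample.

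**Promised summary.** Protocol 9.4.8.2: "Clinically significant changes in the laboratory test parameters will be summarized and listed". SAP 7.9.3 describes no such summary, and SAP Section 8, which records changes from the protocol, does not mention it.

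**ECG.** SAP 7.9.5 has the same last-value rule but adds contingency tables that "summarize the shift from the baseline category to the worst post-baseline value".

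**The concern.** A by-visit table shows one selected value per subject per window. That is reasonable for describing a typical course over time but poor for detecting transient abnormalities, which is why a baseline-to-worst table is usually placed beside it. The SAP does this for ECG and not for laboratory data.

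The minimum and maximum in the by-visit summaries do not close the gap, because they are computed on the values already selected. Flagged listings (SAP 6.6.4) show each abnormal result but give no count by arm.

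This matters more than usual here. Protocol 10.1.6 requires no Data and Safety Monitoring Board, and under SAP 3.4 the unblinded Week 16 analysis, including laboratory tables built to Section 7.9, goes to sponsor management for development decisions. The reader of those tables would want to know how many subjects per arm ever left the normal range for ALT, AST, creatine kinase or neutrophils. All four are in the laboratory panel of Protocol Appendix 11, and the SAP text specifies no table that answers the question.

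**Working it through.** The plan states no figure to reproduce. The check applies the written selection rules to test cases and reads off what enters the shift table.

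**Inputs.** The Week 8 window is days 43 to 70 with nominal day 57 (SAP Table 2). The rules are last value at a visit (SAP 7.9.3), unscheduled values only if the scheduled one is missing and then the most recent (SAP 7.9), and the alternative choice of the nearest on or before the nominal day (SAP 6.2.1, reached through 6.6.1).

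| Case | Results in the window | Value tabulated | Peak kept? |
|---|---|---|---|
| A | Week 8 high; normal repeat on day 60 filed as unscheduled | High | Yes |
| B | Week 8 high; normal repeat on day 60 filed under Week 8 | Normal | No |
| C | Week 8 normal; unscheduled high on day 66 | Normal | No |
| D | Week 8 missing; unscheduled high on day 55 and normal on day 62 | Normal under 7.9; high under 6.2.1 | Depends on the rule |
| E | Week 8 missing; one unscheduled high on day 55 | High | Yes |

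**Reading the cases.**

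- Case C needs no assumption about data entry. A scheduled value exists, so the day 66 result is listed and enters no laboratory summary.
- Cases A and B differ only in the visit label given to the repeat. The protocol and SAP do not say which label is used.
- Case D is a conflict in the text. Day 62 is the most recent, so SAP 7.9 selects the normal value. Day 62 is after day 57 and day 55 is not, so SAP 6.2.1 selects the high value. SAP 7.9 is the more specific rule, but its heading limits it to continuous parameters, while the shift table is categorical. The SAP does not say which rule prevails.

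**Protocol against SAP.** For laboratory data, Protocol 9.4.8.2 promises both a summary and a listing of clinically significant changes, and SAP 7.9.3 carries no such summary. For ECG, the same protocol section promises only listings of clinically significant abnormalities, yet SAP 7.9.5 adds a summary by treatment group and a worst-value shift. SAP 7.9.2 likewise counts adverse events at their worst grade. Laboratory data are the exception.

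**Frequency.** The number of subjects affected depends on the abnormality rate, the share of abnormal results found at unscheduled draws, and the visit label given to repeats. The documents give none of these, so no count is offered.

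**The case against.** The strongest reply is the adverse event route. Protocol 8.2.1.1.1 makes a laboratory result judged clinically significant an adverse event, Protocol 8.2.7 sends clinically relevant changes to the adverse event section of the eCRF, and SAP 7.9.2 tabulates treatment-emergent events by arm. Only clinically significant values must be repeated, so those most exposed to overwriting should reach by-arm tables in another form. This largely stands. A reader might infer that a transient liver or neutrophil signal would appear only in listings, but for clinically significant values the documents say otherwise. The route is still incomplete. It depends on the investigator's judgement, it excludes findings associated with the underlying disease unless more severe than expected, and Protocol 8.2.1.4 prefers the diagnosis to the abnormal test as the reported term. Out-of-range values not judged clinically significant are not covered.

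A reader might also infer that repeat testing systematically removes peaks from the tables. The documents do not support that. Loss by repetition requires the repeat to carry the same visit label. With central laboratory results returning later, a separate unscheduled draw is at least as plausible, and then the scheduled peak stays (case A). Return to normal is also only one of four stopping points for repeats.

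The shift-table wording in SAP 7.9.3 is introduced as an example, and the table shells are in a separate document (SAP Appendix 3). A worst-value table may therefore exist there. What can be said is that the SAP text does not specify one.

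Finally, the last-value rule is conventional and has a use: where a sample is repeated for a technical problem, the later value is the valid one. That argues against replacing the rule with the scheduled draw, and no such replacement is proposed.

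**Conclusion.** The point holds as a gap in safety reporting. Three parts follow from the text alone: an out-of-range value found only at an unscheduled visit enters no laboratory summary when a scheduled value exists in the window; the SAP specifies no baseline-to-worst laboratory shift although it does for ECG; and the protocol's summary of clinically significant laboratory changes is absent from SAP 7.9.3 without being declared in SAP Section 8. The clash between the two rules for choosing among unscheduled values is also explicit. Loss of a peak to a repeat at the same visit is conditional on how repeats are filed.

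The main thing missing is by-arm counts of subjects with out-of-range values, chiefly those not judged clinically significant. The size cannot be computed. It would be going too far to conclude that the tables understate harm by any given amount or favour an arm: the rules apply equally to every arm, the values remain in flagged listings, and the clinically significant ones should appear as adverse events. The change is worth making because it is cheap and uses data already collected.

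**What to change.** 1. In SAP 7.9.3, add shift tables from baseline to the worst post-baseline value, by arm and study period, with low and high handled separately. Use all valid scheduled and unscheduled values, and exclude results superseded because of a technical problem with the sample.
2. Restore the by-arm summary of clinically significant laboratory changes from Protocol 9.4.8.2, or declare and justify its removal in SAP Section 8.
3. State one rule for choosing among unscheduled values in by-visit laboratory tables, and amend SAP 6.6.1 or 7.9 so that they agree. The last-value rule for several results at one visit can remain for the by-visit tables.

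The cost is SAP wording and a few extra tables, with no new data collection. Worst-value tables will show more abnormalities in every arm, so they should be read as comparisons between arms. Excluding technically invalid samples requires the reason for each repeat to be available in the data.

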### 7.9.4 Vital Signs

Summary statistics (n, mean, median, standard deviation, minimum, and maximum) of the raw values and change from baseline for pulse rate, systolic blood pressure, diastolic blood pressure, body temperature, respiratory rate, height, and weight will be tabulated by treatment and visit.

Vital sign measurements (pulse rate, systolic blood pressure, diastolic blood pressure, body temperature, and respiratory rate) during the study will be displayed in a vital signs listing.

### 7.9.5 Electrocardiogram (ECG)

ECG data (Heart Rate, PR Interval, RR Interval, QRS Interval, QT Interval, and QTcF Interval) will be tabulated with descriptive statistics by visit for both the raw values as well as the changes from baseline.

Number and percentage of subjects with clinically significant abnormalities in all ECG parameters will be summarized for normal, abnormal - not clinically significant and abnormal - clinically significant categories by treatment group. Three-by-three contingency tables will be presented to summarize the shift from the baseline category to the worst post-baseline value. Summary results will include the count and percentage of subjects within each shift category and treatment group.

If there are multiple ECG values for the same parameter at a given visit, the last value will be chosen for analysis.

All ECG data as well as clinically significant abnormalities will be presented in by-subject listings.

### 7.9.6 Other Safety Assessments

Chest X-ray, physical examination, TB test results, pregnancy test, viral serology, and FSH will be presented in listings for the Safety Analysis Set. All physical examination results for the subjects with abnormal finding(s) will be listed. No AEs of special interest will be defined.

## 8. CHANGES FROM METHODS PLANNED IN THE PROTOCOL

- The protocol uses the following spelling for the patient global impression questionnaires: “PGIS”, “PGIC”, and “PGIB”. This SAP uses the following spelling for the patient global impression questionnaires: “PGI-S”, “PGI-C”, and “PGI-B”.

- The protocol uses the term ‘major protocol violations’ in the definition of the Per Protocol Analysis Set. This SAP uses the term ‘important protocol deviations’ throughout.
- The protocol states that the primary estimand is comprised of four components. This SAP includes a fifth component, treatment condition, per ICH E9 (R1) addendum.
- The protocol has two secondary endpoints for PGI-C data with titles that begin “Proportion of subjects achieving improvement...”. This SAP uses the following titles to better distinguish between the two: “Proportion of subjects achieving much improvement...”, and “Proportion of subjects achieving improvement...”.

## 9. STATISTICAL SOFTWARE

The statistical software to be used for generation of the tables, listings, and figures is Statistical Analysis System® (SAS) version 9.4 or higher.

## APPENDIX 1 DATA HANDLING RULES

The following table presents the algorithms to be used in SAS to calculate the derived variables, including rules for handling other missing data or partial dates, or irregular/unexpected data issues.

Category	Description	Data Handling Rules
1. Medical History	Medical History Beginning Date of Condition	
 
Missing day of begin date of condition will be imputed as the 1st of the month for the purpose of computing the onset day.
 
Missing month of begin date of condition will be imputed as June for the purpose of computing the onset day
 

	Medical History End Date of Condition	
 
Missing day of end date of condition will be imputed as the 30th of the month for the purpose of computing the onset day.
 
Missing month of end date of condition will be imputed as June for the purpose of computing the onset day
 

2. First and Last Treatment Dates	date/time of first and last dose of a study treatment	The date and time (24 hr. clock) of the first dose of study treatment will be taken from the Dosing eCRF. The date of the last dose of study treatment will be the last date of dosing from the Dosing eCRF for the treatment.
3. Last Visit Date	Date of Last Visit	Date of last visit according to the Visit eCRF.
4. Last Study Participation Date (SDTM variable, typically named RFPENDTC)	Last Study Participation Date (SDTM variable, RFPENDTC), where SDTM denotes Study Data Tabulation Model	Last study participation date is defined as last known date of contact which would be the later of the following dates: last visit date, date of the last dose, date of study completion or discontinuation, or death date.
5. Study Day Definitions	Study Day for assessment/event which occurs on or after the start of study treatment	Study Day = Date of assessment/event – date of the first dose of study treatment + 1.
	Study Day for assessments/events on days prior to the first dose of study treatment in the study	Study Day = date of assessment/event – first dose date of treatment in the study.
	Study Day of Randomization	Study Day of Randomization = date of randomization – date of the first dose of study treatment in the study + 1. Study Day is 1 if baseline day is on the day of randomization.
	First Dose Day	First Dose Day in the study is defined as the study day of the first dose of study treatment in the study (Study Day 1).

Category	Description	Data Handling Rules
	Last Dose Day	Last Dose Day in the study is defined as the study day of the last dose of study treatment in the study (defined as the last date of dosing from the Dosing CRF pages).
	Last Study Day	
For subjects who did not receive study treatment in the study (e.g., Non-Randomized subjects), Last Study Day is defined as (the later of the last visit date and the date of study completion or discontinuation from the End of Study CRF) – Date of Screening Visit + 1.
 
For subjects who received study treatment in the study, Last Study Day is defined as (the later of the last visit date and the date of study completion or discontinuation from the End of Study CRF) – first dose date in the study + 1.

	Days Since Last Dose for event (e.g., Death)	Days Since Last Dose is defined as date of event – date of last dose of study treatment.
6. Duration of event	The duration of any event	The duration of any event is defined as (stop date – start date + 1).
7. Prior and concomitant, medication / treatment	Prior and concomitant medication/treatment	
 
Prior medication/treatment is any medication/treatment stopped prior to the first dose of study treatment (or the date of the randomization visit, Day 1, if the date of the start of study medication is missing). Medication/treatment continued into the treatment period will not be considered prior.
 
A medication/treatment will be identified as a concomitant medication/treatment if any of the following are true: 
 
The start date or the end date is on or after the date of the start of study treatment (or the date of randomization, Day 1, if missing).
 
The medication/treatment is checked as 'Ongoing', and the start date of the medication/treatment is prior to the first dose of study treatment (or the date of the randomization visit, Day 1, if the date of the start of study medication is missing).
 
The start date and the end date are both missing
 
 
 

8. Adverse event	Treatment-emergent adverse event	
If the AE start date is partial/missing, then
 
 
If AE start date is completely missing, then the AE is considered as treatment-emergent.
 
If both AE start month and day are missing and AE start year is the same or after the first dose year, then the AE is considered as treatment-emergent.
 
If AE start day is missing and AE start year and month are the same or after the first dose year and month, then the AE is considered as treatment-emergent.
 

Category	Description	Data Handling Rules
		Missing/incomplete (partial) AE start and end dates will not be imputed for data listings.
	Assignment of TEAE to Placebo-Controlled vs. Extension and Follow Up Period	Report the TEAE in placebo-controlled period if AP01SDT < AESTDTC; Else report the TEAE in extension and follow-up period if AP02SDT < AESTDTC
	Missing relationship to study drug	For TEAE summary by relationship, a TEAE with a missing relationship to study drug will be considered as related.
9. Efficacy	Change from baseline	Endpoint value at Week x – endpoint value at baseline
	Percent change from baseline	(Endpoint value at Week x – endpoint value at baseline)/ endpoint value at baseline
	Scoring rules for DLQI questionnaires	
 
• If one question left unanswered, assign a score of 0 for that question.
 
• If two or more questions are left unanswered the questionnaire is not scored.
 
• For question 7, 
 
◦ “Yes” is assigned a score of 3
 
◦ “Not Relevant” is assigned a score of 0
 
◦ “No” and “A lot” is assigned a score of 2
 
◦ “No” and “A little” is assigned a score of 1
 
 
 

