#### 8.2.1.4 TIME PERIOD AND FREQUENCY FOR EVENT ASSESSMENT AND FOLLOW-UP

The occurrence of an AE or SAE may come to the attention of study personnel during study visits and interviews of a study subject presenting for medical care, or upon review by a study monitor.

All AEs including local and systemic reactions will be captured on the appropriate eCRF. Information to be collected includes event description, date of onset, clinician's assessment of severity, seriousness, relationship to study treatment (assessed only by those with the training and authority to make a diagnosis), action taken, and outcome of the event. All AEs occurring while on study must be documented appropriately regardless of relationship (see [Section 8.2.1.3.2](#)). All AEs will be followed to adequate resolution or stabilization.

Study site personnel will note the occurrence and nature of each subject's medical condition(s) present prior to the informed consent signature in the appropriate section of the source document and eCRF. During the study, study site personnel will note any change in the condition(s) and the occurrence and nature of any AE. Care will be taken not to introduce bias when detecting AEs and/or SAEs. Open-ended and nonleading verbal questioning of the subject is the preferred method to inquire about AE occurrences.

Should a subject experience an AE at any time after the screening visit informed consent signature until the end of participation in the study, the event will be recorded as an AE in the source document and eCRF. Any SAE related to the study participation (eg, screening procedure) will be recorded in the source document and eCRF from the time consent is given to participate in the study until the end of participation in the study (EOS/ET visit).

Investigators are not obligated to actively seek AEs or SAEs after conclusion of the study participation. However, if the Investigator learns of any SAE, including a death, at any time after a subject has been discharged from the study, and he or she considers the event to be reasonably related to the study treatment or study participation, the Investigator must promptly notify the pharmacovigilance unit.

Any medical condition that is present at the time that the subject is screened will be considered as medical history and not reported as an AE. However, if the study subject's condition deteriorates at any time during the study, it will be recorded as an AE.

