#### 9.4.8.1 ADVERSE EVENTS AND SERIOUS ADVERSE EVENTS

A TEAE is defined as:

- A new event that occurs during or after first dose of study treatment or,
- Any event present at Baseline that worsens in either intensity or frequency after first dose of study treatment.

Adverse events will be coded using the MedDRA and only TEAEs will be summarized. Number of events and percentage will be tabulated by preferred term (PT) and primary system organ class (SOC). Multiple occurrences of an AE for a subject will only be counted once per primary SOC and PT. Percentages will be determined relative to the subjects in the Safety Analysis Set for the given treatment arm.

If the intensity or seriousness of the AE changes, the overall intensity or seriousness will be the maximum intensity or seriousness of the multiple occurrences. The TEAEs, SAEs, TEAEs leading to treatment discontinuation, and TEAEs leading to withdrawal of subject will be tabulated for each treatment arm.

All AE data will be listed for each subject.

Summaries over SOC and PT of TEAEs, TEAEs leading to death, SAEs, and TEAEs that led to discontinuation from the study or study treatment will be presented by treatment. Summaries will also be presented by relatedness to the study treatment and the severity of the TEAE.

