### 6.6.3 Adverse Events

AEs experienced by the subjects will be collected throughout the entire study and will be coded using the latest version of the MedDRA specified in the approved Data Management Plan. Analysis of adverse events will be carried out on the Safety Analysis Set during the placebo controlled period and the Extension Analysis Set for the extension period.

An adverse event is considered treatment-emergent if the date of onset is during or after first dose of study treatment, or if the AE present at baseline that worsens in either intensity or frequency after first dose of study treatment. An adverse event that begins on the same date as the first dose of study treatment is treatment-emergent if the AE begins on or after the time of first dose or if the time of AE onset is unknown.

The severity of AEs will be evaluated as “Mild”, “Moderate”, and “Severe” using the criteria specified in [Section 8.2.1.3.1](#) of the study protocol.

AEs will be classified as related, possibly related, unlikely to be related, or unrelated to study treatment using the criteria specified in [Section 8.2.1.3.2](#) of the study protocol.

Adverse events will be categorized as serious or non-serious using the definition specified in [Section 8.2.1.2](#) of the study protocol.

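### SAP Appendix 1 ignores a known pre-dose stop date, so some resolved screening AEs with an incomplete start date are counted as treatment-emergent

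*SAP*

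**What the plan says.** SAP 6.6.3 sends the treatment-emergent decision for partial onset dates to Appendix 1, so item 8 there is the operative rule. It has three branches:

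- Nothing known: "If AE start date is completely missing, then the AE is considered as treatment-emergent".
- Only the year known: the AE is treatment-emergent under the condition "If both AE start month and day are missing and AE start year is the same or after the first dose year".
- Year and month known: the AE is treatment-emergent under the condition "If AE start day is missing and AE start year and month are the same or after the first dose year and month".

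None of the branches refers to the stop date. The one mention of end dates in the item concerns presentation: "Missing/incomplete (partial) AE start and end dates will not be imputed for data listings".

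The definitions these branches are meant to serve are in SAP 6.6.3, "An adverse event is considered treatment-emergent if the date of onset is during or after first dose of study treatment", and Protocol 9.4.8.1, "A new event that occurs during or after first dose of study treatment". Each adds a second route: an event present at baseline that worsens after the first dose.

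AE recording starts before dosing. Protocol 8.2.1.4 covers the span "Should a subject experience an AE at any time after the screening visit informed consent signature until the end of participation in the study", and Protocol 8.2.1.5 has the investigator record both start and stop dates.

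**The concern.** An event that was over before the first dose has neither onset nor worsening after it, so it fails both routes of the definition. Item 8 can still flag it, because it never consults the field that would settle the matter. Presuming treatment-emergence is sensible when timing is unknown. In these records it is known.

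The flag matters because SAP 7.9.2 lists all AEs but summarises only TEAEs. A wrong flag puts a pre-treatment event into the main TEAE table and, where it qualifies, into the serious or severe tables. SAP 3.4 includes AE tabulations in the Week 16 analysis that informs development decisions.

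The same appendix already uses this logic for medications. Item 7 classes a medication stopped before the first dose as prior. The lack of a matching condition in item 8 looks like an oversight.

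**Working it through.** The plan gives no figure to reproduce here. The check applies the three branches as written.

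**Inputs.** The branches: SAP Appendix 1, item 8. The definition: SAP 6.6.3 and Protocol 9.4.8.1. Screening of up to 30 days: Protocol 1.3. Planned arm size of 40: SAP 3.5. Calendar year 2022 and start days spread evenly over a full 30-day window are my assumptions, for illustration.

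**1. One event.** First dose 20 March 2022; AE from 5 to 10 March 2022, stop date recorded. It ended 10 days before dosing.

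| Start date as recorded | Item 8 result | Definition |
|---|---|---|
| 5 March 2022 (complete) | not TEAE | not TEAE |
| March 2022 | TEAE | not TEAE |
| 2022 | TEAE | not TEAE |
| missing | TEAE | not TEAE |

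The rule goes wrong only when the start date is incomplete.

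**2. How often each branch misfires, given such a record.** Take every first-dose date in 2022 with each of the 30 preceding days as the start date, and suppose every AE ended before dosing: 365 × 30 = 10,950 combinations.

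- *Complete start date:* 0 flagged.
- *Day missing:* flagged when the start is in the first-dose month. For a month of L days that is the sum of (d − 1) over d = 1 to L, or L(L − 1)/2: 465 for 31 days, 435 for 30 and 378 for 28. The total is 7 × 465 + 4 × 435 + 378 = 5,373, and 5,373/10,950 = 49%. A quick check with a uniform 30-day month gives 14.5/30 = 48%.
- *Month and day missing:* escapes only when the start falls in 2021, which needs a first dose on 1 to 30 January: 30 + 29 + … + 1 = 465. So 10,950 − 465 = 10,485 are flagged, or 96%.
- *All missing:* 10,950 of 10,950, or 100%.

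These shares are conditional on a record having that pattern of missing data. They say nothing about how common such records are, and the documents do not allow that to be estimated. A screening period shorter than 30 days puts the start nearer to the first dose and raises the 49% and 96%.

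**3. Effect on a table.** One misclassified event in an arm of 40 moves the incidence of its preferred term by at most 1/40 = 2.5 percentage points. The effect is zero if the subject has a genuine TEAE with the same term, because SAP 7.9.2 counts a subject once per term.

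**4. With the stop date used.** If a complete stop date before the first dose makes the AE not treatment-emergent, 0 of the 10,950 combinations are flagged under any of the four patterns.

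**The case against.** The strongest reply is that the affected set is very narrow. The AE must begin after consent, since Protocol 8.2.1.4 treats conditions present at screening as medical history. It must end within at most 30 days, before Day 1. Its start date must still be incomplete after data queries (Protocol 10.1.8 and 10.1.9.1), while its stop date is good enough to place it before dosing. AE summaries are descriptive, no between-arm AE test is planned, and the by-subject listings leave an early stop date visible. SAP Section 1 also allows substantiated departures from the plan. All of this stands. It limits the importance of the point but does not supply the missing condition.

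A second reply is that presuming treatment-emergence is deliberately conservative. That is right when timing is unknown, but it does not justify setting aside a recorded stop date that settles the order.

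A third is that the period-assignment test in item 8 would remove these events. It cannot be relied on to do so. It compares a period start with the AE start date and cannot be evaluated when that date is missing, which is equally true of genuine TEAEs. SAP 6.6.3 also says that TEAEs are tabulated whether or not the onset date is complete.

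A reader might infer more than the text supports:

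- *That screening AEs in general are counted as TEAEs.* Those with a complete pre-dose start date are classified correctly.
- *That the treatment comparison is biased.* The events precede any study drug, so there is no reason for them to favour an arm; they add noise.
- *That the treatment-related tables are routinely inflated.* Under Protocol 8.2.1.3.2 causality is graded partly on timing, so an AE that ended before dosing would ordinarily be graded unrelated or unlikely. It reaches those tables only if graded related, or if causality is left blank and the missing-relationship rule (SAP 7.9 and Appendix 1) makes it related.

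**Conclusion.** The point holds as a minor defect in a stated rule. For an AE with an incomplete start date and a stop date before the first dose, item 8 gives a result contrary to the plan's own definition whenever the start date is wholly missing, or its known month or year matches that of the first dose. Nothing elsewhere in the SAP or protocol corrects it.

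The number of records is unknown and probably small. The 2.5-point figure is an upper bound for one event on one term in one arm, assuming the planned 40 treated subjects. No efficacy result is touched. The change is worth making because it is nearly free, not because the safety conclusions hang on it.

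**What to change.** Add to all three branches of item 8:

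*…unless the AE stop date shows that the event ended before the first dose: a complete stop date earlier than the first-dose date, or a partial stop date whose known year and month (or known year, if only the year is known) is strictly earlier than that of the first dose. If the AE is ongoing, or the stop date is missing or cannot settle the order, the AE stays treatment-emergent.*

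The comparison for partial stop dates must be strict and on like units. With a first dose on 20 March 2022 and a stop date known only as March 2022, the order is undecided and the AE should stay a TEAE. A plain text comparison would sort 2022-03 before 2022-03-20 and drop an event that may have begun after dosing, which is a worse error than the one being repaired.

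The cost is one clause in Appendix 1 and one programming condition. Stop dates are already collected, so no new data are needed, and the conservative default stays wherever timing is unknown.
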